1. SUMMARY

Fetal growth restriction (FGR) is a significant health care issue, affecting 20,000 Australian pregnancies every year ¹. Undetected FGR is one of the key risk factors for stillbirth, but FGR can also cause significant impairments in short and long-term health outcomes for the child. It is a major risk factor for preterm birth and is a recognised causal pathway to the neurodevelopmental injury underlying cognitive and behavioural impairment and cerebral palsy.

Current obstetric care is focused on the detection of the growth restricted fetus and then ultrasound assessment of fetal wellbeing to guide timing of delivery. This approach seeks to maximize the gestational age of the fetus at delivery to minimise the risks of prematurity, while delivering the fetus in time to reduce the likelihood of stillbirth. Currently, *no therapies exist* that can maximize fetal wellbeing in the setting of growth restriction and minimise the frequency of antenatally acquired brain injury due to in-utero hypoxia.

This triple-blind, randomized, parallel group, placebo-controlled trial will administer maternal melatonin or placebo supplementation antenatally in the setting of early-onset severe FGR to determine whether melatonin can PROTECT the fetal brain and lead to improved neurodevelopmental outcomes.

2. BACKGROUND

2.1 Fetal Growth Restriction

In Australia, 1 in 16 babies are born with a low birthweight (<2500g)¹, however many more will have failed to reach their true growth potential. Identifying those babies that are genuinely growth restricted compared to those that are constitutionally small is an ongoing challenge in the field of obstetrics. Currently, many different definitions exist to try and improve our accuracy at identifying those babies unable to reach their growth potential. The definition is important as those babies that are small (traditionally classified at <10th centile) or those failing to achieve their growth potential are at significantly increased risk of stillbirth².

FGR can also cause significant impairments in short and long-term health outcomes for the child. For example, FGR is a major risk factor for preterm birth and is a recognised causal pathway to the neurodevelopmental injury underlying cognitive and behavioural impairment and cerebral palsy³⁻⁶. Indeed, premature growth restricted infants have a 4-6-fold increased risk of cerebral palsy⁴ and are more likely to have persisting structural brain changes, as well as worse neurodevelopmental outcomes^{3,5,6}.

Not surprisingly, the impact of FGR extends beyond the individual child: potentially affecting the health and wellbeing of the parents, as well as having significant economic costs for the healthcare system and broader community. Indeed, stillbirth alone is estimated to cost the Australian economy \$7.6 billion annually⁷, and it is likely that the long-term financial repercussions of FGR are considerably higher.

While the complications of FGR are becoming increasingly understood, many challenges remain. Current methods for the clinical detection of the growth-restricted fetus are limited, particularly for FGR at term. In routine pregnancy care, fetal growth is still determined by measuring the symphyseal-fundal height through abdominal palpation. A measurement more than 2 cm smaller than expected for the gestation suggests FGR. Such an approach, which has been the foundation of pregnancy care for nearly a hundred years, detects, at best, less than half of all cases, and as few as 12-15% of cases in low-risk women⁸. Accurate detection is essential because undetected FGR babies are disproportionately represented in the stillborn population⁸. Where FGR is detected, the rate of stillbirth is halved because of timely intervention, including delivery⁸.

In contrast, early-onset FGR is often more readily diagnosed through identification of growth restriction on the mid-trimester morphology ultrasound or through serial ultrasound assessments of fetal growth in women at high risk of FGR⁹. Therefore, the challenge with term FGR is its detection and diagnosis to enable timely delivery and minimise stillbirth, whereas with early-onset FGR the challenge is the prevention of impaired neurodevelopmental outcomes.

Early-onset FGR has multiple causes, such as underlying genetic abnormalities, environmental events, infections or placental insufficiency ¹⁰. Placental insufficiency is the most common cause of early-onset FGR ¹⁰. In the setting of impaired placentation, the fetus must make a number of compensatory adaptations in order to cope with the inadequate oxygen and nutrient supply. These adaptions serve to protect its vital organs, especially the heart and brain. It is now appreciated, however, that even with these physiological adaptions, significant structural brain changes can still occur.

Evidence derived from multiple animal models has demonstrated that severe FGR, is a significant antecedent to perinatal brain injury ¹¹. It is postulated that the cerebral insult is most likely attributable to the resultant hypoxia-ischaemia as a consequence of placental dysfunction ^{11,12}. Such prolonged compromise can give rise to intracranial haemorrhage (ICH) and periventricular leukomalacia (PVL) (both risk factors for cerebral palsy), as well as white matter hypomyelination and axonal injury ¹³. It is these structural brain changes, which underpin the neurodevelopmental impairment seen in the newborn and infant ^{11,12}. Consequently, these children are at increased risk of cerebral palsy, learning difficulties at school, a lower IQ, as well as problems in executive function, behaviour, and language ^{5,9,14}.

2.2 Pathophysiology

Inadequate placental implantation is a critical feature in early-onset FGR. In early pregnancy, the trophoblastic cells invade and remodel the maternal uterine spiral arteries within the inner third of the myometrial wall. In turn, this alters narrow, high-resistance vessels to lower resistance, dilated vessels capable of delivering the significantly larger volumes of oxygenated blood to the placental bed and developing fetus. If this process is impaired, the spiral arteries are only superficially or partially remodeled within the uterine decidua, blood flow to the placental bed is limited. This leads to ischaemia – reperfusion injuries within the placental bed, upregulation of hypoxia-induced genes and increased production of free radicals secondary to oxidative stress. Clinically, this process is associated with pregnancy loss, FGR and preeclampsia.

Indeed, pregnancy is a time of increased metabolic challenge for both mother and baby, and as such even normal pregnancy is associated with a state of oxidative stress compared with non-pregnancy [15], [16]. The placenta is a key source of this oxidative stress, due to its high metabolic rate and level of mitochondrial activity ^{17,18}. Oxidative stress occurs when the production of pro-oxidant free radical species exceeds the capacity of cells within an organ to neutralize or scavenge them. The capability of placental antioxidant defenses to ameliorate the effects of these potentially damaging free radicals is fundamental for healthy placental function and therefore optimal growth and development of the fetus. While a variety of fetal adaptations exist to allow the fetus to withstand acute or chronic changes in oxygenation, in the setting of impaired placentation, the developing fetus may be exposed to high levels of oxidative stress due to overproduction of oxygen free radicals and a decrease in the mitigating activity of available antioxidants.

Overproduction of reactive oxygen species from any cause leads to a well-described causal pathway of cellular damage through lipid and protein peroxidation, and cell death via apoptotic or necrotic pathways ^{19,20}. The relationship between oxidative stress and proinflammatory processes is also noteworthy ^{21,22}. When immune cells are activated, many produce oxygen free radicals, which in turn incite a further inflammatory response. The developing fetal brain is particularly vulnerable to both free radical-induced damage and systemic inflammatory stressors, and intuitively, in the context of low oxygen availability, the fetus may benefit from novel focused antioxidant neuroprotective strategies.

2.3 Current Clinical Management of Fetal Growth Restriction

Following detection of FGR, current goals in clinical care center on assessment of fetal wellbeing and evidence of a physiological adaption to placental insufficiency. This information guides the timing of steroids, if indicated, and planning of delivery to minimise the likelihood of stillbirth. Magnesium sulphate is the only available therapy shown to improve fetal brain development in the setting of placental insufficiency and hypoxia. Magnesium sulphate works through reducing glutamate release in a hypoxic environment, likely minimising hypoxic brain injury ²³. It appears to reduce the risk of subsequent cerebral palsy by approximately 30% ²⁴. However, magnesium sulphate is only used in the hours immediately before birth, while a significant proportion of underlying brain injury in FGR probably occurs over the preceding days to weeks. The use of a safe, maternally administered supplement commenced in the weeks prior to birth could provide further significant benefits in reducing the complications faced by premature infants in the setting of placental insufficiency.

2.4 Melatonin as an Anti-Oxidant

Melatonin (5-methoxy-N-acetyltryptamine) is an endogenous lipid-soluble hormone produced primarily by the pineal gland in humans. It provides circadian and seasonal timing cues due to neuroendocrine control in response to daylight. As such, melatonin secretion is relatively low during the daytime, with an exponential increase in synthesis and secretion occurring from mid-afternoon and peaking at midnight.

In addition to timing cues, melatonin is a powerful antioxidant, acting both as a direct scavenger of oxygen free radicals, especially the highly damaging hydroxyl radical, and indirectly via up-regulation of antioxidant enzymes including glutathione peroxidase, glutathione-reductase, superoxide dismutase and catalase ^{25,26}. The metabolites of melatonin provide further anti-oxidant effect ²⁷.

To evaluate the maternal-fetal transfer of melatonin Okatani et al. (1998) ³⁷ administered a single oral dose of 3mg melatonin to 33 women at term (37-40 weeks gestation) 1- to 4-hours before a planned caesarean section. Levels of melatonin were evaluated in maternal venous blood and umbilical venous and arterial blood. A total of 12 healthy pregnant women delivered by vaginal birth served as controls. Administration of melatonin led to a rapid (<120 minutes) and marked (>20-fold) increase in the fetal serum levels. There were no differences between maternal and fetal serum levels of melatonin, suggesting a rapid and unrestricted transfer of melatonin from mother to fetus.

The same authors tested whether melatonin could up-regulate antioxidant enzymes ³⁷. No longer than 12 hours before voluntary termination of pregnancy (between 7- and 9-weeks gestation), an oral dose of 6mg melatonin was administered to 47 pregnant women. A significant increase of the antioxidant enzyme glutathione peroxidase was observed in chorionic homogenates derived after the procedure, leading to the conclusion that melatonin might provide an indirect protection against injury caused by reactive oxygen species as seen in preeclampsia, FGR and fetal hypoxia.

The dose used in this trial is based on data from a clinical trial of melatonin for preeclampsia ³⁸ showing that 30mg per day was safe for mother and baby without any apparent adverse effects ³⁹. Venous cord blood concentrations of melatonin achieved were unchanged between a mother receiving 8mg and 30mg per day of melatonin (melatonin concentration ~2100pg/mL). This cord blood concentration would appear sufficient for neuroprotection according to information in sheep models. However, the degree of oxidative stress reduction achieved within the placental bed was less in mothers receiving 8mg melatonin per day. As such, it was felt that the higher dose of 30mg per day was more likely to achieve a clinically significant result.

2.6 Melatonin Use in FGR

Our group has shown that melatonin supplementation exerts multiple anti-oxidant and anti-inflammatory effects, leading to a significant reduction in oxidative stress and lipid peroxidation within the fetal brain in an ovine model of FGR ¹³. In the absence of melatonin, this study showed that lipid peroxidation within the fetal brain led to significant white matter hypomyelination and axonal injury, causing impaired neurological performance in the lambs. Injury was ameliorated entirely in those exposed to melatonin supplementation, with no structural brain injury seen and neurodevelopmental outcomes normalised.

As a result, a small (n=12) phase 1 trial was conducted at Monash Health supplementing pregnancies affected by severe FGR with 8mg of melatonin per day. Melatonin use was well tolerated with no adverse effects seen. A reduction in the degree of placental lipid peroxidation was seen (n=6) ¹³.

3. TRIAL HYPOTHESIS AND AIMS

3.1 Hypothesis:

Improved neurodevelopmental outcomes will be observed in children affected by fetal growth restriction who receive antenatal maternal melatonin supplementation in comparison to those who receive placebo.

3.2 Primary Aim:

The primary aim is to determine whether neurodevelopment at two years of life is improved among survivors of FGR who receive melatonin antenatally compared with those who receive placebo.

3.3 Secondary Aims:

1. To determine the impact of melatonin supplementation on fetal growth and wellbeing.
2. To determine whether antenatal melatonin supplementation in fetal growth restriction is associated with less structural brain injuries at term corrected age.
3. To report the occurrence of any adverse and serious adverse events associated with melatonin use.

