4.3 Potential Risks of Melatonin Treatment

The most common side effects of melatonin are headache, dizziness, nausea and sleepiness ⁴⁵. Melatonin does not have any acute pharmacological effects on the nervous or vascular systems, apart from its benign but active impact on sleep mechanisms ⁴⁶. Extremely high doses of up to 800mg/kg of melatonin were safely administered to animals without deaths, meaning a median lethal dose could not be established. In humans, long-term treatment with high, daily doses of up to 10g melatonin did not cause any toxicity except for isolated cases of cutaneous flushing, abdominal cramps, diarrhoea, scotoma lucidum and migraine ⁴⁷.

Prolonged ingestion of 1g melatonin per day caused only subjective drowsiness but did not provoke any toxicity in the eyes, liver, kidneys and bone marrow ⁴⁸. In a phase II clinical trial conducted in the Netherlands, 1400 women were given 75mg melatonin nightly over 4-years, with no side effects reported ⁴⁹.

The safety of melatonin use in pregnancy was explored in early pregnant Sprague-Dawley rats, at doses ranging from 1 to 200mg/kg/day and did not affect antenatal mortality, fetal body weight or other measures of fetal wellbeing ⁵⁰. Maternal adverse effects seen at high doses, included mild sedation, reduced maternal weight gain and reduced food intake. This study sought to determine the maternal and fetal no adverse effect level (NOAEL). The NOAEL is the exposure level where a particular substance does not statistically or biologically significantly increase the frequency or severity of adverse effects in an exposed population compared to a suitable control population. The maternal NOAEL in this study was found to be 100mg/kg/day, the fetal NOAEL was established at $\geq 200\text{mg/kg/day}$ when administered to the mother. The maternal lowest observed adverse effect level toxicity was 200mg/kg/day. With the above information taken in context, the Australian Therapeutic Goods Administration (TGA) has assigned melatonin a Pregnancy Category B3 classification.

We have recently completed a phase 1 trial (NCT01695070) using melatonin supplementation in pregnancy, as well as a clinical trial in women with pre-eclampsia (ACTRN12613000476730) using the same dose as proposed for this trial, and to date no adverse effects have been identified in the mother, fetus or neonate ^{13,38,51,39}.

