14. OUTCOME MEASURES

14.1 - Primary Outcome

Improved neurodevelopmental performance at 2 years of life among survivors of early onset FGR.

The ability of melatonin to protect the fetal brain in the setting of severe early-onset fetal growth restriction will be assessed by multiple assessments across the first 2 years of life. The trial is powered to detect a difference in neurodevelopmental performance at 24-36 months corrected age on the Bayley-4. Other tools of assessing brain development and neurocognitive performance will also include GMA and MRI at term, GMA again at 3-months corrected age and ITSEA at 24-36 months corrected age. These assessments will also be stratified depending on the fetal gestation and fetal Dopplers at the time of FGR diagnosis, with outcomes for those <28 weeks and between 28-31+6 weeks compared as a sub-analysis. Total mortality will be compared between melatonin and placebo.

14.2 - Secondary Outcomes

- Assessment of drug safety and tolerability: Maternal side effect profiles experienced, such as symptoms of drowsiness, abdominal cramps, flushing, migraines, gastrointestinal disturbance. This information will be collected from the participant medication diary.
- Maternal end-organ performance monitored through haematological and biochemical tests
- Fetal effects through assessing ultrasound parameters of fetal biometry (HC, BPD, AC and FL) and wellbeing (AFI, Doppler indices).

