16. SAFETY ISSUES AND MONITORING

There may be unexpected serious adverse reactions associated with melatonin when used in pregnancy. To date, clinical studies have not demonstrated any serious adverse reactions to melatonin, however metabolic changes during pregnancy may alter the pharmacological properties in unanticipated ways.

16.1 - Eliciting and documenting AE and SAE

The recording of adverse experiences is an important aspect of the trial's conduct. The lead PI responsible for trial-related medical decisions will be designated as the person responsible for the assessment, documentation and reporting of all events to the sponsor, Monash Health, that meet the definition of an AE, SAE or SUSAR. All site PI's are responsible for notifying the lead PI of SAE and SUSAR's as outlined below in section 16.5.

Assessment and reporting will be undertaken in line with the requirements of the Sponsor, Monash Health and the National Health Medical Research Council (NHMRC)⁵⁸. For this trial, it is a stipulation of Monash Health Human Research Ethics Committee (HREC) that if a participant experiences a serious adverse event that is related/possibly related/unknown if related to the study drug, a report will be provided to the HREC and a copy will also be forwarded to the Pharmacy.

All AE/SAE will be recorded from the time of signing the consent form, until the participant has completed all trial related follow-up procedures i.e. until all follow-up visits and assessments of the child at approximately 2 years corrected age have been completed.

All observed or volunteered AE/SAE regardless of causal relationship will be recorded and reported. These events may be declared by the participant or legal guardian and/or identified in response to an open-ended question from the researchers or revealed by observation, physical examination, or while undertaking other trial related procedures.

The researchers are not obligated to actively seek AE/SAE in former trial participants. However, if the lead PI learns of any SAE, including a death, at any time after a participant or their child has been discharged from the trial, and the lead PI considers the event reasonably related to the trial participation, the PI would promptly notify the sponsor, Monash University. For all adverse events as detailed below, a notification email must be sent to [contact], and enrolled patients will be alerted to this.

16.2 – Definitions

16.2.1 - Adverse Event (or Adverse Experience)

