Any untoward medical occurrence in a participant or clinical investigation participant administered a pharmaceutical product and which does not necessarily have to have a causal relationship with this treatment.

An adverse event (AE) can therefore be any unfavourable and unintended sign (including an abnormal laboratory finding, for example), symptom, or disease temporally associated with the use of a pharmaceutical product, whether or not considered related to the pharmaceutical product.

16.2.2 - Adverse Drug Reaction (ADR)

For *marketed pharmaceutical products*, a definition of an adverse drug reaction in the post marketing setting is found in the Australian Code for the Responsible Conduct of Research 59:

“A response to a drug which is noxious and unintended and which occurs at doses normally used in man for prophylaxis, diagnosis, or therapy of disease or for modification of physiological function” p28.

The old term "side effect" has been used in various ways in the past, usually to describe negative (un-favourable) effects, but also positive (favourable) effects. It is recommended that this term no longer be used and particularly should not be regarded as synonymous with adverse event or adverse reaction.

16.2.3 - Serious Adverse Event (SAE) or Adverse Drug Reaction (ADR)

During the conduct of the trial, adverse events may occur which, if suspected to be related to the pharmaceutical product administered (adverse drug reactions), might be significant enough to lead to important changes in the way the pharmaceutical product is used (e.g. change in dose, population, monitoring required, consent forms). This is particularly true for reactions that, in their most severe forms, threaten life or function. Such reactions will be reported promptly to the sponsor, Monash Health and if necessary also the VMIA and TGA.

To ensure no confusion or misunderstanding of the difference between the terms "serious" and "severe," which are not synonymous, the following note of clarification is provided:

The term "severe" is often used to describe the intensity (severity) of a specific event (as in mild, moderate, or severe myocardial infarction); the event itself, however, may be of relatively minor medical significance (such as severe headache). This is not the same as

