These events are reported on the SUSAR/USADE site report available at: <http://www.health.vic.gov.au/clinicaltrials/application-instructions.htm>

All SUSAR that are reported to Research Support Services will require an action plan from the investigator, specifying what action is being undertaken and a follow up report within 30 days of reporting. If Investigators suspect an adverse event may be a SUSAR, they should report it immediately to the TGA.

For SUSAR, it is mandatory to include the UR number, date of birth and participants initials as the SUSAR report is forwarded to the VMIA.

16.5.2 - Serious Adverse Events (SAEs)

All SAE that occur with a Monash Health participant or with a participant from a site that Monash Health has provided HREC Review through multi-site trial approval, which are considered by the investigator as being definitely related, probably related, possibly related and unknown are to be reported within 72 hours to Research Support Services.

These reports for AE and SAE are available at:
<http://www.health.vic.gov.au/clinicaltrials/application-instructions.htm>

All SAE that are reported will require an action plan from the investigator, specifying what action is being undertaken and a follow up report is to be provided within 30 days of the initial report.

SAE should be reported immediately to the sponsor and the TGA, except for those SAE that the protocol identifies as not needing immediate reporting.

In the event of a death of a trial participant, sites should follow local site recommendations in addition to completing an SAE report. For example, for Monash Health participants, it is also mandatory for the death notification to be entered into the Riskman module.

16.5.3 - Adverse Events (AE)

The reporting of AE is at the discretion of the investigator based on whether the investigator is concerned that the adverse event poses a safety risk.

In addition, if the researchers or the sponsor is of the opinion that an adverse event, which is not graded 3 or above but poses a safety risk, should also be reported. Adverse events must be reported to the Research Support Services, Monash Health within 60 days of the date of the researcher learning of the event. These reports are available at:

<http://www.health.vic.gov.au/clinicaltrials/application-instructions.htm>

16.6 - Line Listings

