It may be the events may occur that are not related to the trial or therapeutic intervention. Such as, prolongation of hospitalisation for a reason that is not related to trial participation e.g. social reasons. The details surrounding these events will be assessed by the Lead Principal Investigator and if deemed not-related, they will not be reported. The details of these events will however be stored.

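### Sections 16.1, 16.5.3 and 16.9 disagree on which adverse events are reported, and secondary aim 3 does not settle whether all events are compared by arm

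*Protocol*

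**What the plan says.** **Aim.** The only safety aim is the third secondary aim in Protocol Section 3.3: "To report the occurrence of any adverse and serious adverse events associated with melatonin use". The primary aim in Section 3.2 names the placebo group as comparator; aim 3 names none.

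**Capture.** Section 16.2.1 defines an adverse event as something that follows use of the product in time, "whether or not considered related to the pharmaceutical product". Section 16.1 states: "All observed or volunteered AE/SAE regardless of causal relationship will be recorded and reported".

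**Reporting.** Section 16.5.3 states: "The reporting of AE is at the discretion of the investigator", with concern about a safety risk as the criterion. Section 16.9 covers events thought to have nothing to do with the trial or the intervention. The Lead Principal Investigator assesses them and "if deemed not-related, they will not be reported", although the details are kept.

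**Safety committee.** Section 16.7.2 lists interim data on trial-related adverse events as a review item. It then advises the committee to stop or re-evaluate the trial if either arm shows a statistically significant rise, or a rise of 50% over baseline, in adverse events of any kind. Under Section 16.7.5 the Lead Principal Investigator tells the committee about the events that have been sent to the sponsor.

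**Outcomes and analysis.** Section 14.1 compares total mortality between the arms. Section 14.2 lists maternal side effects from the diary, maternal laboratory tests and fetal ultrasound measures. Section 15 compares outcome measures by arm on an intention-to-treat basis.

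**The concern.** A placebo arm allows harm to be judged by counting all events in each arm, without anyone deciding what caused each one. That advantage is lost if events must first be judged related before they are counted.

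The risk is greater in this population because the disease offers a ready explanation for many serious events. Sections 4.1 and 4.2 give pre-eclampsia in 15 to 40% of these women, caesarean delivery for about 97% of growth-restricted infants born before 32 weeks, and serious neonatal morbidity in around 30% of survivors. Section 16.4 tells raters to take the natural history of the disease into account. Section 10.1 keeps the research team blinded, so the rater cannot see whether events are gathering in one arm.

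At stake are what the safety committee receives during the trial and what the final safety result covers. If Section 16.9 is followed rather than 16.1, a difference between arms in events put down to the disease could be understated in both.

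**Working it through.** The protocol gives no figure on this point to reproduce, so the check compares the passages.

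1. **16.1 against 16.9.** Section 16.1 promises both recording and reporting, whatever the cause. Section 16.9 withholds reporting when the cause is judged unrelated. On recording they agree, since 16.9 stores the details. On reporting they cannot both be followed for the same event.

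2. **16.1 against 16.5.3.** The first has every adverse event reported. The second makes reporting a matter of discretion. Section 16.5 as a whole concerns reports to the sponsor, so the two could be reconciled if 16.5.3 covers only individual notification. The protocol does not say so.

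3. **The route to the safety committee.** The advised rule in 16.7.2 needs counts of all events by arm. The notification in 16.7.5 is of events sent to the sponsor, and 16.5.3 and 16.9 decide which events those are. The listed review item in 16.7.2 is also limited to trial-related events. The rule and the information described for it therefore differ in scope.

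4. **Other reports.** Section 16.6 asks for a periodic line listing of all serious events, which agrees with 16.1 but leaves out non-serious events and does not say how 16.9 events are handled. Section 17 limits progress reports to events attributed to trial participation.

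5. **Aim 3.** Its phrase can mean events occurring in association with being allocated melatonin, or events attributed to melatonin. Aim 2 supports the first meaning: "To determine whether antenatal melatonin supplementation in fetal growth restriction is associated with less structural brain injuries at term corrected age" is plainly a between-group question. Aim 3, however, sets out to report events rather than to determine whether an association exists. Both readings are open.

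6. **Sections 14 and 15.** The between-arm analysis in Section 15 applies to outcome measures. Section 14 names total mortality and maternal side effects, but no outcome consisting of all adverse and serious adverse events, so Section 15 does not clearly reach them.

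**Direction of the effect.** Let the true difference in an event rate between arms be d, and suppose a share f of events is judged related, the same in both arms because raters are blinded. A filtered count then shows a difference of f × d. With f = 1 nothing is lost; as f approaches 0 the difference disappears. The protocol gives no value for f, and any power figure would depend on the value assumed, so none is offered.

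**The case against.** The strongest reply is that the protocol never says its safety result is restricted. A reader might infer from aim 3 that only events attributed to melatonin will be reported, so that a real excess put down to the disease would not appear. The documents do not support that:

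- Aim 3 contains no word such as *only* and no causality test.
- The definition in 16.2.1 includes events "whether or not considered related to the pharmaceutical product", and aim 2 uses the same phrase for a group association.
- Total mortality is compared by arm with no attribution, so perinatal loss is not exposed to any filter.
- The committee's advised rule covers any adverse events in either arm.
- Section 16.5.3 sits under sponsor notification. The example in 16.9 is a hospital stay prolonged for social reasons, and the details are stored.
- A table of adverse events by arm is commonly specified in a statistical analysis plan, which is not shown here.

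All of this stands, and it limits the point. It does not remove the conflict between 16.1 and 16.9, which is in the protocol text. The social-reasons example does not confine 16.9, whose operative words apply to any event judged unrelated. Nor does the committee's rule cure the problem, because the information described for it may be narrower than the rule.

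**Conclusion.** The point holds as a contradiction in Section 16 together with an ambiguous aim. The protocol does not fix whether events judged unrelated are reported, and so whether they reach the safety committee and the final comparison of arms. Severity is minor.

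This rests on two readings: that reporting in 16.9 includes reporting to the sponsor, and that the committee relies on the notification described in 16.7.5. If it receives complete tables of all recorded events by arm through another route, the consequence during the trial falls away and only the wording needs repair.

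It would go too far to say that an excess of harm would be hidden. Events are recorded or stored, so an excess stays in the data and can be found; the protocol simply does not secure that it is counted. Nor is the symptom list in Section 14.2 part of the point: it is given as examples, and the diary and questionnaire items are not shown.

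**What to change.** 1. In Sections 16.5.3 and 16.9, state that discretion and judged relatedness govern expedited reporting only. Say that every event recorded under 16.1, including those stored under 16.9, is held in the trial database and counted.
2. In Sections 16.7.2 and 16.7.5, state that the committee receives all recorded adverse and serious adverse events by arm, prepared so that the trial team stays blinded. Remove the limitation to trial-related events from the review item.
3. Reword aim 3: *to compare all adverse and serious adverse events between the melatonin and placebo arms, regardless of attributed cause*. Show attributed events as a supplement.

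The cost is wording in Sections 3.3, 16.5.3, 16.7 and 16.9 and one additional table. No new data are needed, though events stored under 16.9 may have to be coded. The downside is a longer table made up mostly of events due to the disease. On the timeline in Section 18, recruitment was to end in December 2023, so the committee's scheduled reports at 100 and 200 participants may already have been made; the change to the final comparison would still be useful.
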